13.7.2.2. Handling of Missing data for Statistical Analysis

Element	Reporting Detail
Snapshot	
 In the Snapshot dataset, subjects without HIV-1 RNA data in the assessment window for the visit of interest (due to missing data or discontinuation of IP prior to the visit window) do not belong to 'HIV-1 RNA < 50 c/mL (or <200 c/mL)'. The nature of this missing data will be further classified in Snapshot summaries as either 'HIV-1 RNA ≥ 50' or 'No Virologic Data at Week X'; Appendix 11: Snapshot Algorithm Details for full details
LOCF	
 In the LOCF dataset, missing values will be carried forward from the previous, non-missing available on-treatment assessment. If the baseline value is missing any missing values until the first non-missing value will remain missing.
Lipid LOCF	
Baseline for Lipids LOCF Analyses:
 
 Last evaluable lipids assessment up to and including the start of IP, where 'evaluable' is defined as: Lipid modifying agents not taken within 12 weeks of the date of assessment and Lipids are collected in a fasting state. Subjects with unevaluable Baseline for Lipids (as defined above) will be excluded from this dataset.

Element	Reporting Detail
	
Post-Baseline:
 
 ● If subjects initiate serum lipid-lowering agents Post-baseline, then the last available fasted On-treatment lipid values prior to the initiation will be used in place of future, observed On-treatment values. ● Imputation at visits with observed on-treatment values will continue even if the subject discontinues the lipid-lowering agent. Missing assessments will not be imputed 
Analyses Evaluated with Lipid LOCF dataset:
 
This dataset will be used to summarize fasting lipids parameters in the following displays:
 
 ● Summary of Chemistry Values by visit ● Summary of Chemistry Change from Baseline by visit ● Summary of TC/HDL ratio Change from Baseline. ● All other displays of lipids (i.e. toxicity tables and NCEP tables) will use observed fasting data, without LOCF imputation

13.8. Appendix 8: Values of Potential Clinical Importance

Element	Reporting Detail
Laboratory Values and Adverse Events	

• The central laboratory will flag lab parameter toxicities directly in the provided datasets based on Division of AIDS Table for Grading the Severity of Adult and Paediatric Adverse Events Version 2.0, November 2014

13.9. Appendix 9: Population Pharmacokinetic (PopPK) Analyses

PopPK will be described in a separate document.

13.10. Appendix 10: Pharmacokinetic / Pharmacodynamic Analyses

PK/PD dataset specification and methodology will be described in a separate document.

13.11. Appendix 11: Snapshot Algorithm Details

Detailed Algorithm Steps

- Consider an analysis visit window for Week X (e.g. Week4, ...Week 24, Week 48 et al). The Window for Week 24/48 visit is defined in Table 11 (e.g. window for Week 48 is ± 6 Week: $295 \leq \text{Study Day} \leq 378$) and in Table 9 for other visits through to Nominal Week 52 at Maintenance Phase. The Snapshot Analysis at post Maintenance Phase will not be appropriate because a large portion of responders will be switched to other studies and not all subjects would have the chance to reach same timepoint.
- The HIV1-RNA threshold of 50, 200 copies/mL will be analysed, respectively, in this study
- The analysis window 'Week 48' and HIV1-RNA threshold of '50 copies/mL' are used for the purpose of illustration. A subject's Snapshot response and reason at Week 48 are categorized as below.
 - HIV1-RNA < 50 copies/mL
 - HIV1-RNA ≥ 50 copies/mL
 - Data in window not below 50
 - Discontinued for lack of efficacy
 - Discontinued for other reason while not below 50
 - Change in background therapy*
 - No Virologic Data at Week 48 Window
 - Discontinued study due to AE or death
 - Discontinued study for other reasons
 - On study but missing data in window

* Note: since changes in ART are not permitted in this protocol, all such subjects who change ART during the maintenance phase will be considered 'HIV1-RNA ≥ 50 copies/mL'. if the change in ART is made prior to an analysis timepoint. Subjects with protocol permitted oral bridging treatment will not be considered ' HIV1-RNA ≥ 50 copies/mL' due to 'change in ART'.

- The steps in determining response and reasons are indicated in Table below, in the order stated.

Detailed steps		
Please note that the following scenarios will NOT be penalized Per Snapshot algorithm (i.e. please excluding these scenarios from Condition 1-4).		

 • Dose reduction, dropping a component, or change in formulation (e.g. 'Tivicay + Kivexa' to 'Triumeq' with the identical ingredients) 		
Condition ('Week 48' indicates Week 48 window)	Response	Reasons
1. If non-permitted change in background therapy prior to Week 48	HIV1-RNA ≥ 50	Change in background therapy
2.If permitted change ^[a] in background therapy prior to Week 48 AND the latest on-treatment VL prior to/on the date of change is ≥ 50 c/m (NA to this study)	HIV1-RNA ≥ 50	Change in background therapy

Condition ('Week 48' indicates Week 48 window)	Response	Reasons
3: If non-permitted change in background therapy during Week 48		

 Last on-treatment VL during Week 48 prior to/on the date of change ≥ 50 c/mL 	HIV1-RNA ≥ 50	Data in window not below 50

 Last on-treatment VL during Week 48 prior to/on the date of change <50 c/mL 	HIV1-RNA < 50	

 No VL during Week 48 prior to/on the date of change 	HIV1-RNA ≥ 50	Change in background therapy
4: If permitted change ^[a] in background therapy during Week 48 AND the last on-treatment VL prior to/on the date of change is ≥ 50 c/mL (NA to this study)		
4.1 this last on-treatment VL occurs prior to Week 48	HIV1-RNA ≥ 50	Change in background therapy
4.2 this last on-treatment VL occurs during Week 48 but prior to/on the date of change	HIV1-RNA ≥ 50	Data in window not below 50
5: If none of the above conditions met		
5.1 VL available during Week 48		

 Last on-treatment VL during Week 48 ≥ 50 c/mL 	HIV1-RNA ≥ 50	Data in window not below 50

 Last on-treatment VL during Week 48 <50 c/mL 	HIV1-RNA < 50	
5.2 No VL during Week 48		
if subjects still on study, i.e. the upper bound of analysis snapshot window is prior/equal to the following date Current ART arm: Min (Current ART Stop Date + 1, withdrawal date) IM Q4W arm: Min[max(Date of last Q4W IM Dose + 35, Date of last oral dose+1), withdrawal date]	No virologic data at Week 48 Window	On study but missing data in window

Condition ('Week 48' indicates Week 48 window)	Response	Reasons

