7.1.5.1. Statistical Methodology Specification

Primary Statistical Analyses
Endpoint

 Proportion of Participants with Plasma HIV-1 ≥ 50 c/mL at Week 48 using the Snapshot algorithm for the ITT-E population. ‘HIV-1 RNA≥ 50’ are based on the Snapshot algorithm includes subjects who had plasma HIV-1 RNA ≥ 50 c/mL at Week 48, who discontinued for lack of efficacy, who discontinued for other reasons while not < 50 c/mL, or who changed ART).
Snapshot Dataset

 Virologic outcome (‘HIV-RNA < 50’ or ‘≥ 50 copies/mL’) per Snapshot algorithm is determined by the last available on-treatment HIV-1 RNA measurement within the analysis visit window of interest (please refer to analysis window defined in Table 11). In addition, subjects who discontinue for reasons not related to adverse event with on-treatment HIV-1 RNA result at the time of discontinuation ≥ 50 copies/mL or who change study treatment not permitted per protocol during maintenance phase before the analysis visit are classified as ‘HIV-RNA ≥ 50 copies/mL’. Full details of the Snapshot algorithm are provided in Section 13.11.
Model Specification

 The primary efficacy endpoint will be analysed using a stratified analysis with Cochran-Mantel-Haenszel (CMH) weights, adjusting Baseline third agent class (PI, INI, or NNRTI) and sex at birth The CMH estimate of the adjusted treatment difference will be calculated as a weighted average of strata-specific estimates of the treatment difference calculated within each of the following Baseline analysis strata resulting from the cross classification of both stratification factors: 
 Baseline third agent class PI AND Male sex at birth Baseline third agent class PI AND Female sex at birth Baseline third agent class INI AND Male sex at birth Baseline third agent class INI AND Female sex at birth Baseline third agent class NNRTI AND Male sex at birth Baseline third agent class NNRTI AND Female sex at birth If n_k is the number of CAB LA + RPV LA treated subjects, m_k is the number of the control arm treated subjects, and $N_k = n_k + m_k$ is the total number of subjects in the kth stratum, then the CMH estimate is given by $\hat{d}_{cmh} = \frac{\sum W_k \hat{d}_k}{\sum W_k}$ 
where

Primary Statistical Analyses

$$W_k = \frac{n_k m_k}{N_k}$$

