02	
Subject has non-compliance with IP (including IM dosing errors) or took/received incorrect IP (i.e., other than the one to which they were randomized) that is:
 
Maintenance phase
 
 1. > 10% of total time on-treatment with under dosing deviations up to the analysis timepoint of interest (e.g. Week 48). 2. Two or more injection intervals affected by over dosage deviations (e.g. extra injection or excessive volume administered, length of time between injections less than 3 weeks, excluding split doses) up to the analysis timepoint of interest. 
For this purpose, the total number of non-compliant under dosing days up to the analysis timepoint of interest, is derived as follows:
 
 • Control Arm: 
 a. Interruptions of control arm ART for reasons other than treatment-related adverse events/laboratory abnormalities (based on concomitant ART eCRF forms); • Q4W IM Arm: 
 a. Length of time until next injection from date of dosage/administration deviation potentially resulting in under dosage (e.g. 1ml administered instead of 2ml) b. Length of time between injections exceeding 5 weeks (e.g. missed or late

Number	Exclusion Description
	
injection visit) for post Week 12 and exceeding 4 weeks for Week 8 and Week 12
 
c. Interruptions of oral lead-in or oral bridging (if necessary) for reasons other than treatment-related adverse events/laboratory abnormalities (based on eCRF Exposure forms);
 
Note: The total no. of under dosage non-compliance days will be derived based on the above rules and censored at the date of last on-treatment viral load for the visit of Week 48 snapshot analysis during Maintenance phase.

03	
Prohibited medications: receiving ART medication other than that prescribed/allowed by the study (excluding permanent changes in ART regimen; such cases will be retained as 'HIV1-RNA≥50 c/mL' in the per protocol snapshot analysis) or receiving prohibited concomitant medication that would impact exposure or response to therapy with duration and route of administration taken into consideration, as recorded in the Protocol Deviation form in the eCRF based on study team review (where indicated in the PDMP as case-by-case determination)

04	
Permanent discontinuation of IP/withdrawal due to a reason of "Protocol Deviation" (as recorded in the eCRF Conclusion form).

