13.3.2. Definitions of Assessment Windows for Data Other than Health Outcome and PK

Table 9 Assessment Windows for Screening & Maintenance Phase Data

Parameters[d] collected in sparse visit [c]	Analysis Window	Target Study Day	Analysis Timepoint
	Study Day ≤ 1 (the first record if there are multiple values)	The day of earliest record	Screening
	Last available recorded value up to and	1	Baseline

Parameters[d] collected in sparse visit [c]	Analysis Window	Target Study Day	Analysis Timepoint
	including the date of first maintenance phase dose of IP		
ECG, CD8, CD4/CD8 ratio	2 ≤ Study Day ≤ 70	29	Week 4
	2 ≤ Study Day ≤ 42		
	43 ≤ Study Day ≤ 70	57	Week 8
	71 ≤ Study Day ≤ 98	85	Week 12
	99 ≤ Study Day ≤ 126	113	Week 16
	127 ≤ Study Day ≤ 154	141	Week 20
urinalysis, CD8, CD4/CD8 ratio	155 ≤ Study Day ≤ 210	169	Week 24
	155 ≤ Study Day ≤ 182		
	183 ≤ Study Day ≤ 210	197	Week 28
	211 ≤ Study Day ≤ 238	225	Week 32
	239 ≤ Study Day ≤ 266	253	Week 36
	267 ≤ Study Day ≤ 294	281	Week 40
	295 ≤ Study Day ≤ 322	309	Week 44
	ECG, CD8, CD4/CD8 ratio, urinalysis, lipids, bone and renal markers	323 ≤ Study Day ≤ 378	337
323 ≤ Study Day ≤ 350			
	For 'Current ART' arm; 351 ≤ Study Day ≤ Maintenance Current ART Stop Day ^[b] + 1 For 'Q4W' arm: 351 ≤ Study Day ≤ Max (Day of Last Q4W IM Dose + 35, Last Oral dose Day + 1) ^[a]	365	Week 52
	For subjects who discontinued from oral lead-in during Maintenance phase, Study Day > (Day of last oral lead-in dose+1) Subjects discontinued from Current ART and not continuing into extension phase Study Day > (Maintenance Current ART Stop Day ^[b] + 1)		Follow-up

[a] Last Q4W IM / last oral dose is only applied to subjects who permanently discontinue from study treatment

[b] Current ART stop day: the last permanently stop day among all ARTs taken during Maintenance phase.

[c] For parameters with sparse collection, post baseline data will only be slotted to those specific analysis windows. The Screening or Baseline slotting will be based on the same rules as all other lab parameters use.

[d] **Urinalysis:** Urine Albumin/Creatinine, Urine Creatinine, Urine pH, Urine Protein/Creatinine, Urine Erythrocytes, Urine Specific Gravity, Urine Leukocytes, Urine Retinol Binding Protein, Urine Phosphate, Urine Creatinine

Bone marker: Bone Specific Alkaline Phosphatase, Osteocalcin, Procollagen 1 N-Terminal Propeptide, Vitamin D, Type I C-Telopeptides

Renal marker: Cystatin C, Retinol Binding Protein

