	Q4W IM Arm: For subjects continuing into Extension Phase: Maintenance Treatment Start Date < Date ≤ Date of Nominal Week 52 visit For subjects not continuing into Extension Phase: Maintenance Treatment Start Date < Date ≤ LTFU ART Start Date
Extension	Subjects Switching from Maintenance Current ART Arm to Q4W IM: Start Date of Extension Phase Oral lead-in of CAB + RPV < Date ≤ LTFU ART Start Date Subjects continuing maintenance Q4W IM into Extension phase Date of Nominal Week 52 Injection < Date ≤ LTFU ART Start Date

- Date = start or assessment date
- Maintenance Treatment Start Date: refer to Treatment Start Date in Section 13.6.1

Table 18 Assignment of Study Phases for Concomitant medication/ART

Concomitant during:	Date range
Maintenance	Current ART Arm: Maintenance Treatment Start Date ≤ Medication Taken < Start Date of Extension Phase Oral CAB + RPV (expected to be Nominal Week 52) or Withdrawn date prior to Extension Phase
	Q4W IM Arms: For subjects not continuing into Extension Phase: Maintenance Treatment Start Date ≤ Medication Taken < LTFU ART Start Date For subjects continuing into Extension Phase: Maintenance Treatment Start Date ≤ Medication Taken < Date of Nominal Week 52 visit
Extension	Date of nominal Week 52 visit ≤ Medication Taken < LTFU ART Start Date

Note: ART stopped on or before the Maintenance Treatment start date will not be assigned to the Maintenance Phase; ART stopped on or before the date of nominal Week 52 visit will not be assigned to Extension phase.

If a partial date for medication/ART is recorded in the eCRF, the following convention will be used to assign the medication:

- if the partial date is a start date, a '01' will be used for missing days and 'Jan' will be used for missing months;
- if the partial date is a stop date, a '28/29/30/31' will be used for the missing day (dependent on the month and year) and 'Dec' will be used for the missing month; for medications recorded separately in the eCRF as prior ART, the earlier of this imputed date or the day before IP start will be used.

The recorded partial date will be displayed in listings.

Table 19 Assignment to Long-Term Follow-Up Phase

Study Phase	Date range
Long-Term Follow-Up	Date > max(Last IM Injection Date, Last Oral Bridging End Date)

- Date = Assessment/Start Date

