5.2.1 If subjects withdraw before/during Week 48 due to		
5.2.1.1 Safety reasons (e.g. AE/death, liver chemistry stopping criteria, renal toxicity withdrawal criteria, QTc withdrawal criteria et al, as recorded in eCRF Conclusion form)	No virologic data at Week 48 Window	Disc due to AE/death
5.2.1.2 Non-safety related reasons (e.g. Lack of efficacy, protocol deviation, withdrew consent, loss to follow-up, study closed/terminated, investigator discretion et al, as recorded in eCRF Conclusion Form)		

 • Last on-treatment VL <50 c/mL OR no on-treatment VL available during study 	No virologic Data at Week 48 Window	Disc for other reasons

 • Last on-treatment VL ≥ 50 c/mL AND withdrawal due to Lack of efficacy 	HIV1-RNA ≥ 50	Disc. for lack of efficacy

 • Last on-treatment VL ≥ 50 c/mL AND withdrawal due to all other non-safety related reasons 	HIV1-RNA ≥ 50	Dis. for other reason while not below 50

a: Excluding permitted change in background therapy where change or decision to change is made prior to/on the first on-treatment viral result

Examples from FDA guidance

Data in Window

Virologic outcome should be determined by the last available measurement while the patient is on treatment and continued on trial within the time window:

- HIV-RNA = 580 copies/mL at Day 336, HIV-RNA below 50 copies/mL on Day 350. This should be categorized as HIV-RNA below 50 copies/mL.

No Data in Window

Discontinued study due to Adverse Event or Death:

- Any patient who discontinues because of an AE or death before the window should be classified as *Discontinued due to AE or Death* (as appropriate), regardless of the HIV-RNA result, even if the HIV-RNA is below 50 copies/mL at the time of discontinuation.
- However, if a patient has an HIV-RNA value in the time window and also discontinues in the time window, the viral load data should be used to classify the patient's response. This is the Virology First hierarchy:
 - a. HIV-RNA below 50 copies/mL at Day 336 and discontinues because of AE or even dies on Day 360 — this person is categorized as having HIV-RNA below 50 copies/mL.

- b. HIV-RNA is 552 copies/mL on Day 336 and the patient discontinues on Day 360, the patient is categorized as having HIV-RNA greater than or equal to 50 copies/mL.

Discontinued for Other Reasons:

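### In the primary endpoint, Appendix 11 and Table 18 together classify replacement ART around discontinuation differently for control, oral lead-in and injected participants

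*SAP*

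**What the plan says.** - **Order of steps.** Appendix 11 (section 13.11) states: "The steps in determining response and reasons are indicated in Table below, in the order stated". Condition 1 makes a non-permitted change in background therapy before Week 48 a failure. Step 5, which holds all the discontinuation rules, applies only if no earlier condition is met.
- **Scope of the change rule.** The note in Appendix 11 says that "all such subjects who change ART during the maintenance phase will be considered" failures if the change precedes the analysis timepoint. It exempts permitted oral bridging. A separate list exempts dose reduction, a dropped component and a change of formulation. Section 7.1.5.1 words the rule as covering participants "who change study treatment not permitted per protocol during maintenance phase before the analysis visit are classified as" failures. None of these texts says whether ART started after permanent discontinuation is a change.
- **Phase bounds for ART.** Table 18 (section 13.4.1) ends maintenance in the control arm at the start of Extension oral CAB + RPV "or Withdrawn date prior to Extension Phase". For Q4W participants who do not enter the Extension Phase it reads "Maintenance Treatment Start Date ≤ Medication Taken < LTFU ART Start Date", with no alternative bound at withdrawal.
- **Who enters LTFU.** Under section 2.3, only participants with at least one dose of CAB LA and/or RPV LA enter LTFU, and HAART is planned there.
- **Discontinuation for safety.** The step beginning "5.2.1.1 Safety reasons (e.g. AE/death, liver chemistry stopping criteria" gives no virologic data. The example on adverse events in the same appendix agrees, whatever the HIV-1 RNA result.
- **Stop date.** Table 9, footnote b, defines the Current ART stop day as "the last permanently stop day among all ARTs taken during Maintenance phase".
- **Per-Protocol population.** Criterion 03 in section 13.1.1 covers ART outside the study's allowance, "excluding permanent changes in ART regimen; such cases will be retained as" failures.

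**The concern.** A participant who stops randomised treatment usually needs another regimen. Whether starting it is a virologic failure should follow from one stated rule. Here it follows from where Table 18 happens to end the maintenance phase, and that end point differs by arm and by whether an injection was given.

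This affects the primary endpoint of an open-label non-inferiority trial. A suppressed control participant counted as a failure raises the control rate and favours non-inferiority. A suppressed lead-in dropout counted as a failure raises the Q4W rate and works against it. The only sensitivity analysis listed for the primary endpoint is the Per-Protocol analysis. It keeps permanent ART changes as failures, so it does not test the classification.

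**Working it through.** **1. Trace one case through the rules.** Take a suppressed participant who stops for an adverse event well before Day 295, starts another regimen and has no viral load in the Week 48 window (Days 295 to 378). Table 18 is taken as the operative definition of the maintenance phase, because it is the table that assigns ART to phases.

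| Participant | Is the new ART inside maintenance (Table 18)? | Step that decides | Outcome |
|---|---|---|---|
| Control, ART started before the withdrawn date | Yes | Condition 1 | ≥50 |
| Control, ART started on or after the withdrawn date | No (strict inequality) | 5.2.1.1 | No virologic data |
| Q4W, stopped in oral lead-in | Yes, literally: no LTFU ART start date and no other bound | Condition 1 | ≥50 |
| Q4W, injected, LTFU HAART | No: its start closes the phase | 5.2.1.1 | No virologic data |
| Q4W, injected, non-permitted ART before LTFU ART start | Yes | Condition 1 | ≥50 |

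The clinical sequence in rows 1, 3 and 4 is alike, yet the outcomes differ. Rows 1 and 3 also conflict with step 5.2.1.1 and the adverse-event example.

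**2. The plan's own figures.** The SAP gives no figure for this point. The nearest is Table 22, the predictive probability at the futility interim. With Beta(0.5, 0.5) priors, 143 per arm at the interim, 285 per arm at the end and an unpooled test against 6% at 1.96, all 72 cells reproduce to the printed decimal. With 8 failures on CAB, one more control failure (1 to 2) moves the probability from 14.5% to 25.3%, across the 15% trigger. Appendix 14 applies the same data handling to the interim unless otherwise stated.

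**3. Effect of one participant.** N = 570 randomised 1:1 (section 2.3) gives 285 per arm, and 1/285 = 0.35 percentage points.

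**4. Effect near the margin.** The event counts are assumed, and the bound is an unstratified Wald bound that ignores the planned CMH stratification:

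U = (p1 − p2) + 1.96 × √[p1(1 − p1)/285 + p2(1 − p2)/285], with p1 for Q4W and p2 for control.

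For 14 versus 4: p1 = 0.0491, p2 = 0.0140, difference 0.0351, standard error 0.0146, so U = 0.0351 + 0.0286 = 6.37%.

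| Direction | Q4W failures | Control failures | U | Against 6% |
|---|---|---|---|---|
| Control switchers added | 14 | 4 | 6.37% | fails |
| | 14 | 5 | 6.09% | fails |
| | 14 | 6 | 5.82% | passes |
| | 14 | 7 | 5.54% | passes |
| Lead-in dropouts added | 9 | 4 | 4.20% | passes |
| | 10 | 4 | 4.64% | passes |
| | 12 | 4 | 5.51% | passes |
| | 14 | 4 | 6.37% | fails |

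**5. Effect on the error rate, control side only.** Suppose the true difference under a common rule is exactly 6%, the control rate is 2% to 4% (assumed), and a further share r of control is counted as failures. Then P(declare non-inferiority) = Φ(r/SE − 1.96). For a control rate of 2% and r = 1%: SE = √(0.08 × 0.92/285 + 0.03 × 0.97/285) = 0.0190, which gives Φ(−1.43) = 7.6%. Over the 2% to 4% range the probability rises from 2.5% to 4.2–4.6% (r = 0.5%), 6.6–7.6% (r = 1%) and 14–17% (r = 2%). Lead-in reclassification would offset this.

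**The case against.** The case on the other side has real substance.

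- **Control replacement ART is not always a failure.** Table 18 cuts it off at the withdrawn date. If that date is recorded as the day treatment stopped, the interval in which a switch counts may be short. This stands: only ART started before that date is affected, and the SAP does not show how often that happens.
- **The events are not identical.** HAART after an injection is planned, whereas a control participant who switches while still on study has made the change that the guidance examples in Appendix 11 place in the ≥50 row. This also stands, and the fix must keep that rule. It does not settle the case of a participant who is leaving for an adverse event.
- **The lead-in result comes from a missing bound, not an explicit rule.** That is so. The adverse-event example points the other way, so the text supports two answers.
- **The cases would be visible.** Table 2.4 reports Snapshot reasons and Listing 37 lists ART changes. The key secondary endpoint (HIV-1 RNA <50 c/mL) is unaffected, since both outcomes are non-response. This limits the harm, but seeing the cases after the fact does not pre-specify how they count in the primary test.

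A reader might infer that injected participants can never fail through an ART change. They can, if non-permitted ART precedes the LTFU ART start, and they can also fail on viral load. A reader might also infer that the rules tilt the trial towards non-inferiority, or that most of the margin is at risk. If 1% to 4% of control (3 to 11 participants) were affected, the control rate would rise by 3/285 = 1.1 to 11/285 = 3.9 points, or 18% to 64% of the 6-point margin. That range is only an assumption, and the lead-in effect runs the other way.

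**Conclusion.** The concern holds in a bounded form. Following the stated order of steps and the Table 18 bounds gives arm-dependent and phase-dependent classifications of replacement ART in the primary endpoint. Two of these conflict with the SAP's own step for safety withdrawals. This is more than missing detail, because the text as written produces the discrepancy.

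The size is 0.35 points per reclassified participant, and the net direction is unknown. In the assumed examples, two control switchers or five lead-in dropouts reverse the conclusion; results far from 6% would not change. The conclusion rests on reading the maintenance phase in Appendix 11 as Table 18 defines it. Condition 1 itself names no phase, and the protocol, which is not at hand, may say more about which changes are permitted.

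The stop-date definition is secondary. Where Condition 1 already decides the outcome it changes nothing. Once such participants are sent to step 5, however, a replacement regimen that extends on-treatment status under Table 20 could bring in viral loads taken on the new drugs.

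**What to change.** Before the randomisation codes are released:

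1. In Appendix 11, state one rule for control, lead-in dropouts and injected participants on whether ART started at or after permanent discontinuation of randomised treatment is a change in background therapy. Tie it to a recorded discontinuation date and reason. Reconcile it with step 5.2.1.1, the guidance examples and the non-permitted-change rule for participants who switch while still on study. An exemption triggered merely by stopping the Day 1 regimen would be too loose, because it could excuse control switchers whom the examples count as failures.
2. In Table 18, add a withdrawal bound for Q4W participants with no LTFU ART start date.
3. Define the Current ART stop date so that a replacement regimen does not extend on-treatment status.
4. Add one sensitivity analysis of the primary endpoint that applies the alternative classification identically in both arms: any replacement ART before Day 295 counts as ≥50.

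The cost is SAP wording and a little programming. The control failure count may fall, which would make the non-inferiority result slightly less favourable.
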